### **III. Study Design:**

- A. Provide an overview of your study design and methods. The study design must relate to your stated aims/objectives. Details will be requested later. If your study also involves analysis of existing data, please complete Section XI, "Secondary Data Analysis of Existing Data" in the last part of this research plan. If your study ONLY involves analysis of existing data, please use the research plan template for secondary data analysis (JHSPH IRB Research Plan for Secondary Data Analysis of Existing Data/Specimens).

A phase 3, two-arm, single-blind, individual randomized clinical trial will be conducted in the outpatient department of Holy Family Hospital (HFH) in Rawalpindi, Pakistan, to evaluate the impact of the HMHB intervention on the prevalence of CMDs at six weeks postpartum. We will enroll 1200 eligible women, individually randomizing them to either the intervention (i.e., HMHB) or control (i.e., routine care with similar frequency/timing of visits). Each woman randomized into the HMHB intervention arm will be assigned to a HMHB non-specialist provider who will deliver six individual and between two and six booster sessions of the HMHB intervention program. Women allocated to the control condition will receive routine care, but with increased contact so that frequency of contact will match between the study arms. The primary endpoint is the combined prevalence of GAD and MDE at six weeks postpartum. Data on outcome measures will be collected at birth, and at six weeks postpartum by a trained assessment team masked to the allocation status of the study participant (single-blind). All analyses will use an intent-to-treat (ITT) approach, using all subjects randomly assigned to intervention or control groups. We will also evaluate mediators and moderators of the intervention as well as the cost-effectiveness of the HMHB intervention compared with control arm.

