The intervention (i.e. the HMHB sessions) will be provided by non-specialist providers, who will receive simplified training followed by regular supervision.(37) These trainers will have a university degree in the social sciences, at least one year of relevant work experience and knowledge of the local language, but no prior experience in mental healthcare delivery. During year one of the funded grant, they have received a six-day training. Further training will include practice in the field and regular group supervision. The data collection team ('assessors') and non-specialist providers ('trainers') will be continually monitored. During the training period, data collectors will be assessed for interrater reliability (IRR).

Enhanced Usual Care (EUC) Control Group: Women allocated to the control condition will receive EUC. The WHO recommends eight antenatal visits for a positive pregnancy experience(43) which we will be the target number of visits for EUC participants (depending on their gestational week). Visits will involve evaluating health status, discussing any concerns, and performing routine exams consistent with stage of pregnancy. For EUC medical staff at the hospital will receive additional mental health training. Transportation will also be provided or facilitated for participants to assist with attending appointments and up to two ultrasounds will be paid for by the study.

Healthy Controls (HC): For the purpose of this revised application we will add a 2nd control group of 100 women who have low or no anxiety or depressive symptoms (<8 on both the anxiety and depression sub-sections of the HADS). This will allow us to compare biological processes in a group of anxious women with the intervention, a group of anxious women without the intervention and compare them to these healthy controls (non-anxious or depressed, without the intervention).

All three Groups: All medical staff will be trained on the WHO Mental Health Gap Action Programme (mhGAP) curriculum on management and intervention for common mental disorders. Transportation will be reimbursed or provided for women in all three study arms and participants will be offered 400 rupees (\$4) or a mobile phone "top up" voucher of 400 rupees for participation. Participants will also be reimbursed the cost of ultrasounds indicated by their medical team at Holy Family Hospital.

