For only women in this 'revised' biological R01 study: All 300 women (intervention, EUC, and healthy control) in the supplement grant application will receive baby gifts (up to \$10) at the completion of the study as a thank you.

During our preliminary formative research (IRB #7678) during the last year, we conducted in-depth interviews with expectant mothers experiencing anxiety (n=19) and health professionals (n=10) to identify risk factors, means of expressing anxiety, current coping strategies, and the acceptability and feasibility of a facility-based intervention targeting anxiety among expectant women. The content and strategies employed by HMHB are informed by the findings of our

formative study and other relevant literature. Evidence-based strategies for managing anxiety and behavior activation are used in HMHB. Psychosocial risk factors of anxiety such as adverse life events, interpersonal problems, lack of social support, pregnancy complications, and fear of labor are addressed in the intervention.

The dosage of the HMHB is informed by evidence from the literature. The United Kingdom National Institute for Health and Care Excellence (NICE) guidelines recommends between five and seven individual CBT-based sessions for anxiety management. Recent systematic reviews of CBT-based perinatal anxiety interventions indicate that 6 to 12 sessions were effective in reducing symptoms of perinatal anxiety.(99, 100) The HMHB intervention consists of six core sessions and between two and six booster sessions. Core sessions focus on (1) psycho-education and stress management, (2) personal wellbeing, (3) social support, (4) mother-infant bonding during pregnancy, (5) relapse prevention, and (6) preparation for the baby and early postnatal period. The first five core sessions will be delivered weekly to ensure that expectant women receive maximum dosage as early in their pregnancy as possible. The sixth session will be delivered later, in the third trimester. Booster sessions will be delivered during the expectant women's routine antenatal visits to the hospital between the fifth and sixth core sessions. Based on at what gestational week a woman is recruited into the study, each woman will receive between two and six booster sessions. Sessions will last between 45 minutes and an hour. Family member/s will be invited to attend the first, third, and sixth core sessions

Table 1 indicates the active ingredient and timing of each session for the intervention arm.

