**Table 2: Description of Usual Care\***

Visit	Content	Timing of visits as per WHO recommendation	Recipients
Visit 1:	Assessment for anemia; dietary counselling about healthy eating and keeping physically active during pregnancy; folic acid supplements; counseling for common physiological symptoms; emphasizing eight antenatal care visits	Following recruitment	All participants recruited into the study (intervention and control arm)
Visit 2:	Assessment for anemia; dietary counselling about healthy eating and keeping physically active during pregnancy; Iron and folic acid supplements; vaccination; counseling for common physiological symptoms; emphasizing eight antenatal care visits	Second trimester	All participants recruited into the study (intervention and control arm)

Visit 3:	Assessment for anemia; dietary counselling about healthy eating and keeping physically active during pregnancy; Iron and folic acid supplements; vaccination; counseling for common physiological symptoms; emphasizing eight antenatal care visits	Second trimester	All participants recruited into the study (intervention and control arm)
Visit 4:	Assessment for anemia; dietary counselling about healthy eating and keeping physically active during pregnancy; Iron and folic acid supplements; counseling for common physiological symptoms; emphasizing eight antenatal care visits	Third trimester	All participants recruited into the study (intervention and control arm)
Visit 5:	Assessment for anemia; dietary counselling about healthy eating and keeping physically active during pregnancy; Iron and folic acid supplements; counseling for common physiological symptoms; emphasizing eight antenatal care visits	Third trimester	All participants recruited into the study (intervention and control arm)
Visit 6	Assessment for anemia; dietary counselling about healthy eating and keeping physically active during pregnancy; Iron and folic acid supplements; counseling for common physiological symptoms; emphasizing eight antenatal care visits	Third trimester	All participants recruited into the study (intervention and control arm)
Visit 7	Assessment for anemia; dietary counselling about healthy eating and keeping physically active during pregnancy; Iron and folic acid supplements; vaccination; counseling for common physiological symptoms; emphasizing eight antenatal care visits	Third trimester	All participants recruited into the study (intervention and control arm)

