Visit 8	Assessment for anemia; dietary counselling about healthy eating and keeping physically active during pregnancy; Iron and folic acid supplements; vaccination; counseling for common physiological symptoms	Third trimester	All participants recruited into the study (intervention and control arm)

\*Women will also get ultrasound scans as is medically indicated during their prenatal visits. There is typically one in the 2nd and another in the 3rd trimester, but these (and any other additional scans) will occur at the visit/s that the doctor indicates.

In addition to the HMHB information/counseling that is provided to individuals in the intervention arm (Table 2) and the routine information/care provided to those in both the intervention and control arm (Table 3), study procedures also include four data collection timepoints (Baseline, Late Pregnancy, Delivery/Birth, and 6 weeks Post Partum). Procedures that participants will undergo in each of these visits are equivalent between the two study arms, and are summarized below both in brief textual narrative, and in Table 4.

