The proposed study is a single-blind, individual randomized clinical trial. The assessment team, trial statistician, and PIs will be masked to allocation status of study participants. To maintain masking during the trial, intervention and assessment teams will not have any interaction during the trial, as they will be placed at separate locations within the Obstetrics Department of HFH. Furthermore, participants will be instructed not to disclose which type of treatment they are receiving to the assessment team. Fidelity of masking will be measured by having assessors guess the trial arm of each participant at the end of follow-up assessment. We hypothesize that assessors will only be able to correctly guess the condition of participants at a chance rate of nearly 50% at follow-up assessments, indicating that masking is maintained.

2. Will participants receive standard care or have current therapy stopped?

Each woman randomized into the HMHB intervention arm will receive the HMHB intervention program plus usual care. Women allocated to the control condition will get usual care (slightly enhanced) alone. The WHO recommends eight antenatal visits for positive pregnancy experience (43) which we will be the target number of visits for study participants in the control group (depending on their gestational week). These visits will involve evaluating health status, discussing any concerns, and performing routine exams consistent with stage of pregnancy. Usual care will also be enhanced by medical staff at the hospital receiving additional training in mental health treatment to counsel participants. Transportation will also be provided or facilitated for participants to assist with attending appointments and the study will pay for any ultrasounds needed.

3. Will you use a placebo or non-treatment group, and is that justifiable?

The control arm will receive a slightly enhanced version of usual care, which we consider is justifiable.

4. Explain when you may remove a participant from the study.

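### The design overview says contact frequency will match between arms, but the detailed plan gives both arms the same eight target antenatal visits and adds the HMHB sessions to one arm only

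*Combined protocol and SAP*

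**What the plan says.** The overview in Section III.A describes the comparator as "control (i.e., routine care with similar frequency/timing of visits" and adds that controls get routine care "with increased contact so that frequency of contact will match between the study arms". The same paragraph gives the HMHB arm "six individual and between two and six booster sessions of the HMHB intervention program".

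The detailed text is in Section V:

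- **Length and timing of HMHB sessions (Study Implementation and Table 1).** "Sessions will last between 45 minutes and an hour". Core sessions 1 to 5 are weekly and core session 6 comes in late pregnancy. Boosters are held at routine antenatal visits between core sessions 5 and 6.
- **Visit target.** Eight antenatal visits are named as the number "which we will be the target number of visits for EUC participants", subject to gestational age.
- **Who gets the eight visits (Table 2).** The recipients entry for every visit is "All participants recruited into the study (intervention and control arm"). The paragraph after the table again speaks of "routine information/care provided to those in both the intervention and control arm".
- **How the arms differ (therapeutic-intervention questions, item 2 on standard care).** "Each woman randomized into the HMHB intervention arm will receive the HMHB intervention program plus usual care". Control women get the modestly enhanced usual care and nothing further.
- **Enhancements.** Mental health training of medical staff and transport support are listed for all study groups, not for controls only.

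**The concern.** The overview presents contact frequency as a feature that the design holds equal. The detailed sections give one arm everything the other arm gets, plus a programme of individual sessions. Both descriptions cannot be right.

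This matters for attribution. If contact really matched, a lower prevalence of common mental disorders under HMHB could more readily be credited to the cognitive-behavioural content. If it does not match, the trial estimates the effect of the whole package, including time and attention from a dedicated provider. The Mediation Analysis section names stress and social support among the primary mediators, and several hours of one-to-one contact could plausibly move both. A reader who relies on the overview would interpret a mediated effect too narrowly.

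**Working it through.** The plan gives no total number of contacts per arm, so there is no stated figure to reproduce. The totals below are counted from the plan's own components.

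**Inputs**

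- Antenatal visits: 8 in each arm, as a target (Table 2).
- Core sessions: 6, HMHB arm only (Section III.A, Table 1).
- Boosters: 2 to 6, HMHB arm only, held at antenatal visits (Study Implementation, Table 1).
- Session length: 45 to 60 minutes (Study Implementation).

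**Step 1. Sessions and provider time in the HMHB arm**

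- Sessions = core + boosters: 6 + 2 = 8, up to 6 + 6 = 12.
- Minimum time = 8 × 45 min = 360 min = 6 hours.
- Maximum time = 12 × 60 min = 720 min = 12 hours.
- HMHB-provider time in control: none planned.

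**Step 2. Planned contacts, HMHB against control**

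Attendances in the HMHB arm = 8 + 6 + boosters − sessions that share an antenatal visit.

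| Assumption | HMHB | Control | Gap | Ratio |
|---|---|---|---|---|
| Every session counted as its own contact | 16 to 20 | 8 | 8 to 12 | 2.0 to 2.5 |
| Boosters inside antenatal visits (as the plan says) | 8 + 6 = 14 | 8 | 6 | 1.75 |
| Also core sessions 1 and 6 on antenatal visits (assumed) | 14 − 2 = 12 | 8 | 4 | 1.5 |
| Also visits 2 and 3 coinciding with weekly sessions (assumed) | 12 − 2 = 10 | 8 | 2 | 1.25 |

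The last row is generous. It uses four of the eight visits for core sessions and leaves 8 − 4 = 4 for boosters, so it can hold only for women with at most four boosters. Five or six boosters would need one or two further attendances. The residual gap arises because the five weekly sessions are set against only three visits that Table 2 places before the third trimester.

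**Step 3. Does anything in the control arm offset this?** The detailed text describes no control contact beyond the eight visits. Staff training and transport apply to all groups, so they do not narrow the difference.

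**Step 4. Does the sample size depend on it?** No. With 30% against 21% (a 30% relative reduction), 85% power and an assumed two-sided 5% level, the usual two-proportion formula gives 420 per arm, as stated, and 420 / (1 − 0.30) = 600 enrolled per arm. Contact is not an input.

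**The case against.** The strongest defence is that the plan promises little and is candid elsewhere. It speaks of frequency of contact and visits, not of matched minutes or matched therapeutic attention. The primary objective compares the intervention with usual care only. Section III.A justifies the lightly enhanced comparator by its relevance to policy makers, and item 2 on standard care sets out the additive contrast. On this view one loose clause in an overview does no harm.

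Much of this stands:

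- A reader might infer that the plan claims an attention control and fails to provide one. The documents do not support that. The term never appears, and nowhere does the plan say that the trial isolates content from contact.
- A reader might infer that controls have no provider contact. That is also unsupported. Their visits include discussion of concerns, with medical staff who have had extra mental health training. What they lack is HMHB-provider contact.
- A reader might treat the six core sessions as a minimum number of additional attendances. The plan does not say that they are separate from antenatal visits. Six is an upper figure once boosters are placed inside routine visits.
- Some contact data are already planned: session number and attendance as fidelity indicators for HMHB, complier average causal effects by sessions attended, and service-use data in both arms in the third trimester and at six weeks postpartum.

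The defence does not remove the contradiction. The matching sentence directly follows the description of the HMHB sessions and uses the word contact without restriction. The eight-visit target is worded for control women in several places, which may show that a balance was intended, but Table 2 gives the same visits to HMHB women. The overlaps considered above narrow the gap without closing it.

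**Conclusion.** The point holds as an inconsistency between the Section III.A overview and the detail in Section V. The plan states a design property that its own schedule does not deliver. The difference is 8 to 12 sessions, or 6 to 12 hours of HMHB-provider time. In separate attendances it is up to six, about four or about two, depending on how far core sessions are assumed to coincide with antenatal visits. These are planned counts. Eight visits is a target that varies with gestational age, so attended numbers may be lower in both arms.

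A reader might go further and conclude that the comparison is flawed. The documents do not support that. HMHB added to enhanced usual care, compared with enhanced usual care, is a legitimate pragmatic contrast. Randomisation, the endpoint, the intention-to-treat set and the sample size are unaffected. The consequence is confined to attribution: as detailed, the trial cannot separate the programme's content from the additional contact. The documents do not show which text is authoritative.

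**What to change.** 1. Reconcile Section III.A with Study Implementation, Tables 1 and 2 and item 2 on standard care. Either remove the matching statement, together with the description of similar visit frequency, or describe the control contacts that would achieve it. The choice belongs to the investigators.
2. Unless control contacts are added, state in the analysis section that the estimated effect is that of HMHB plus enhanced usual care against enhanced usual care, and that it includes the extra provider contact. Carry the same caveat into the mediation analysis.
3. In the primary report, tabulate by arm the antenatal visits, total contacts and provider time actually attended. Count a booster held at an antenatal visit as one attendance, and record its time separately.

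If the statement is removed, the cost is wording, one descriptive table and a less favourable statement about attribution. Visit and contact attendance must be recorded in the same way in both arms, since the planned session indicators cover HMHB only. No change to randomisation, the primary test or the sample size is needed.

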In our study, the unit of randomization is an individual woman, with an equal number of women randomized to the intervention and control groups. We assume an outcome prevalence of CMDs (postnatal depression episode and anxiety) at 30%, which is conservative given that most estimates of prenatal depression in Pakistan are higher than this. (16, 17, 91, 129) While we observed a 50% reduction in postnatal depressive symptoms when evaluating our prior CBT intervention (which was initiated late in pregnancy), we desire 85% power to detect reductions in CMDs as low as 30% (86, 130, 131), requiring 840 pregnant women (420 in each arm). Anticipating 30% attrition post enrollment, we will enroll 600 women per group in this study, for a total of 1200 women. This sample size of 420 outcomes per group provides ample power to detect important reductions in SGA, which we currently estimate to occur in approximately 47% of births. For example, we will have 90% and 80% power to detect reductions of 23.7% and 20.2%, respectively.

Sample size considerations for the qualitative process evaluation/COVID-questions will be based on a target number of up to 80 women sampled across different characteristics, or until saturation is achieved. We will sample up to 45 women from the intervention group and 25 women from the EUC group and another 10 who dropped out of the intervention. As described (See under Study Design above), these women will be purposively sampled to achieve a wide range of variation (or maximum variation) on various dimensions of interest. To triangulate and learn from multiple perspectives, we will also hold 2 focus group discussions (FGDs) with the HMHB therapists and assessors/screeners involved in delivery, assessments, or coordination of the intervention to ask them about their perspective on the same issues. Topics of interest for sub-group analyses include the effects of transitioning from in-person to by-phone format during the COVID pandemic, distress related to COVID-19, and the effects of prior miscarriage on current pregnancy and intervention experience.

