For the secondary biological study, a sample size of 60 subjects in each group, women with anxiety (with and without intervention) and healthy controls, will give us at least 80% power to detect a difference in means of log-transformed cytokines across groups with an effect size of 0.3 to 0.5. This calculation assumes four repeated measurements with exchangeable covariance structure, a correlation of 0.6 and alpha level = 0.05. The smallest observed effect size for CCL3 between anxious and non-anxious women in the preliminary data of 51 women was 0.3 in 1nd trimester to 0.5 in the 2nd trimester (Cohen's D from 0.3 to 0.5). Sample size calculations were performed using the PASS Sample Size Software program.(34) Prior studies in our clinic have an attrition rate of up to 20%, but because the attrition rate for this type of study in Pakistan is unknown we will increase our sample size to account for higher attrition (up to 40%). We will therefore enroll 300 women to yield an ultimate sample size of at least 180.

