#### **IV. Participants:**

Describe the study participants and the population from which they will be drawn. Specify the inclusion and exclusion criteria. If you plan to include children, note their ages and whether you will include children in foster care. Note if the participants are particularly vulnerable in terms of cognitive limitations, education, legal migration status, incarceration, poverty, or some combination of factors.

Pregnant women attending the outpatient Obstetrics Department of HFH for antenatal care will be approached to determine interest in screening for possible eligibility and participation in the study. Women expressing interest will be asked to provide **consent for screening**, because our screening procedures include a formal assessment using the Hospital and Anxiety Depression Scale (HADS) (see inclusion criteria #6) and the depression component of the Structured Clinical Interview for DSM-5 (SCID) (see exclusion criteria #1). Those providing consent to be screened, will be assessed for eligibility to the intervention and enhanced usual care groups using the below inclusion and exclusion criteria:

- **Inclusion Criteria:**

1. ability to understand Urdu
2.  $\leq 22$  weeks' gestation
3. age  $\geq 18$  years
4. residence  $\leq 20$  km of Holy Family Hospital
5. intent to reside in the study areas until the completion of the study
6. score  $\geq 8$  on the HADS anxiety

- **Exclusion Criteria:**

1. Current major a depressive episode (MDE on SCID) or life-threatening health conditions including e.g. active severe depression or suicidal ideation
2. Self-reported past or current significant learning disability
3. Self-reported past or current psychiatric disorder (e.g. bipolar disorder or schizophrenia) or psychiatric care (e.g. current use of anxiolytic drug and/or other psychotropic drug)
4. medical disorders or severe maternal morbidity that require inpatient management that would preclude participation (e.g. eclampsia, pre-eclampsia, and antepartum hemorrhage)
5. ICU admission (indicated by diagnosis not admitted only for assessment)

For the healthy control group, unique to the biological substudy, inclusion and exclusion criteria will be as above, except that participants must score  $< 8$  on the HADS anxiety.

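### The 30% control-arm CMD rate is called conservative without support for the women enrolled; it could err either way, the 85% power has no slack, and the unadjusted primary test leaves power unused

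*Combined protocol and SAP*

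**What the plan says.** Section III.B of the protocol sets the control rate: "We assume an outcome prevalence of CMDs (postnatal depression episode and anxiety) at 30" per cent, "which is conservative given that most estimates of prenatal depression in Pakistan are higher than this". No other reason is given for the choice. The target follows: "we desire 85% power to detect reductions in CMDs as low as 30" per cent, "requiring 840 pregnant women (420 in each arm"). Losses are then added: "Anticipating 30% attrition post enrollment, we will enroll 600 women per group in this study".

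Section IV lists as the first exclusion "Current major a depressive episode (MDE on SCID"), and also excludes self-reported past or current psychiatric disorder or psychiatric care. Section V.B (Screening Procedures) gives the SCID depression module to women with a HADS depression score of 8 or more. Section VII confirms that depressed cases are excluded at screening. Section IV also requires a HADS anxiety score of at least 8. Section II says that the trial means to treat GAD as well as prevent it, so GAD at entry is not a bar. Section III.A makes the combined six-week prevalence of GAD and MDE the primary endpoint.

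The analysis plan (Section V, Analysis of Primary Efficacy Endpoint) uses Fisher's exact test for the primary comparison. Regression that controls for baseline characteristics is left to sensitivity analysis.

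**The concern.** The reason given for calling 30% conservative concerns a different time (pregnancy rather than six weeks after birth). As worded, it also concerns a different condition, one that the trial largely removes at screening. Nowhere do the documents estimate the six-week GAD or MDE rate among anxious pregnant women without current MDE. A reader of Section III.B would take 85% as a floor on power, and nothing in the text supports that.

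This matters because, for a fixed relative reduction, power depends strongly on the control rate. Since that rate is uncertain, power that can be had at no cost should be taken. The planned unadjusted Fisher test does not take it.

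**Working it through.** **Inputs.** From Section III.B: control rate 0.30; 30% relative reduction, so 0.21 on intervention; power 85%; 420 evaluable per arm; 30% attrition; allocation "with an equal number of women randomized to the intervention and control groups". The section gives no alpha or sidedness for the main trial. Two-sided 0.05 is my assumption; the only alpha stated is for the biological substudy ("a correlation of 0.6 and alpha level = 0.05"). I read the endpoint as either diagnosis being present.

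**Reproducing the plan's figure.**

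n per arm = [1.960·√(2·p̄·(1−p̄)) + 1.036·√(p1(1−p1) + p2(1−p2))]² / (p1−p2)²

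With p̄ = 0.255, the first term is 1.960·√0.37995 = 1.208 and the second is 1.036·√0.3759 = 0.635. Then (1.208 + 0.635)² / 0.09² = 419.6, so 420 per arm. Attrition: 420/0.70 = 600 per arm, 1200 in all. Both match exactly, so the arithmetic is sound and the assumed alpha fits it.

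**Power at other control rates.**

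Power = Φ{[(p1−p2)·√n − 1.960·√(2·p̄·(1−p̄))] / √(p1(1−p1) + p2(1−p2))}, with p2 = 0.7·p1.

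Example at p1 = 0.20: p2 = 0.14 and p̄ = 0.17, giving (0.06·20.494 − 1.960·0.5312)/0.5295 = 0.356, and Φ(0.356) = 63.9%.

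| Control rate | Power, 420 per arm | Exact Fisher, 420 per arm | Power if all 600 per arm are evaluable |
|---|---|---|---|
| 40% | 95.8% | 95% | 99.3% |
| 35% | 91.6% | 90% | 97.9% |
| 30% | 85.0% | 83% | 94.8% |
| 25% | 75.8% | 73% | 88.9% |
| 20% | 63.9% | 61% | 79.1% |
| 15% | 49.8% | 46% | 64.7% |

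The documents give no rate for this population, so the rows are a range and not estimates.

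**Which way the rate might err.** Downward: the MDE and psychiatric-history exclusions; the mental-health training of medical staff and the referral of women who develop depression, which also reach controls (Sections V and VII). Upward: every randomized woman has a HADS anxiety score of at least 8; GAD at entry is kept; GAD counts in the endpoint; and Section II says that prenatal anxiety symptoms persist and strongly predict postpartum disorder. The documents do not allow these to be netted out.

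**What adjustment could recover.** I simulated 20,000 trials per setting with 420 women per arm. HADS was a standardized normal covariate, its log-odds effect on CMD was assumed to be 0.4 or 1.0 per standard deviation, and intercepts were set so that the marginal rates were as stated. The adjusted test was the Wald test for arm in the logistic model.

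| Rates | Fisher (exact) | Adjusted, log-odds 0.4 | Adjusted, log-odds 1.0 |
|---|---|---|---|
| 30% vs 21% | 83.3% | 86.4% | 90.0% |
| 20% vs 14% | 60.6% | 65.3% | 70.1% |

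The gain is about 3 to 7 points in the first row and 5 to 10 in the second. Of that, about 2 points and 3 to 4 points respectively come simply from leaving Fisher's test, because unadjusted logistic regression gave about 85% and 64%. The rest comes from HADS.

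**The case against.** A reader might infer that excluding MDE pushes the rate below 30%, so that the trial is underpowered. The documents do not support that. It takes only half of the eligibility rules. Selection for anxiety, retained GAD and a GAD-inclusive endpoint all push the other way, and at a control rate of 35% or 40% power exceeds 90%. The MDE exclusion may also be incomplete, since the SCID goes only to women with a raised HADS depression score.

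The cited support may not be depression alone. Section III.B cites references 16 and 17, which Section II cites for prenatal anxiety of 49% and 35%. The printed reference list ends at 50 and follows another numbering, so this cannot be settled. Even so, those figures describe anxiety in pregnancy, not diagnoses at six weeks postpartum.

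A reader might also infer that a null result would mean little. That goes too far. Section III.B plans for a 30% reduction after citing a 50% reduction in depressive symptoms in an earlier programme. That was another measure, so it is context only, but for a halving of CMD, power at 420 per arm is 98% at a 20% control rate and 93% at 15%. Losses below 30% would also offset part of any shortfall, as the last column of the power table shows.

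All of this stands. It limits the point to an unsupported label and a primary test that can be improved. It does not supply the missing justification for 30%.

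**Conclusion.** The calculation is correct, but the description of its main input is not supported. The text does not show that 30% is conservative for the women this trial enrols, and the direction of any error is unknown. Because 420 per arm is exactly what 30% versus 21% requires, any control rate below 30% puts power for a 30% reduction below 85% at the planned attrition, and any rate above 30% raises it. Over 15% to 40%, power runs from 49.8% to 95.8%. With the test actually planned, it is about 83% even at 30%.

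These figures assume two-sided 0.05 and a constant 30% relative reduction. The gain from adjustment assumes a prognostic strength that the documents do not give. Enrolled women all score 8 or more, so the spread of HADS is narrowed and the true gain could be smaller than simulated.

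**What to change.** **Analysis plan (Section V, Analysis of Primary Efficacy Endpoint).** Make the primary comparison of six-week CMD a logistic regression on arm, adjusted for the screening HADS anxiety score as a pre-specified continuous term. From it, report a marginal risk difference or risk ratio with its confidence interval. Keep Fisher's exact test as the supporting analysis.

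**Section III.B.** Delete the word conservative. Show power at control rates of about 15% to 40%, and state alpha and sidedness. If Fisher's test stays primary, quote its power (about 83% at 30%) instead of 85%.

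**Cost.** No extra women, visits or data: Table 4 already schedules HADS anxiety for everyone at screening, and it is an eligibility score, so it should be complete. The Missing Data section says that the statistical analysis plan is finalized before unblinding, so the change can still be made there. The price is a model-based primary analysis in place of an exact test, which is why Fisher's test is kept beside it. I do not ask for a blinded check of the pooled CMD rate, because the plan attaches no sample-size or other decision to it.
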